8.3 Serious Adverse Events

An SAE is defined as any untoward medical occurrence that at any dose:

- Results in death
- Is life-threatening (i.e., the participant was, in the opinion of the Clinical Investigator, at immediate risk of death from the event as it occurred); it does not refer to an event which hypothetically might have caused death if it were more severe
- Requires or prolongs inpatient hospitalization
- Results in persistent or significant disability/incapacity (i.e., the event causes substantial disruption of a person's ability to conduct normal life functions)
- Results in a congenital anomaly/birth defect
- Requires intervention to prevent permanent impairment or damage
- Is an important and significant medical event that may not be immediately lifethreatening or resulting in death or hospitalization, but based upon appropriate medical judgment, may jeopardize the patient/participant or may require intervention to prevent one of the other outcomes listed above

AEs that do not fall into these categories are defined as non-serious. It should be noted that a severe adverse event need not be serious in nature and that a SAE need not, by definition, be severe.

In addition, a pre-existing event or condition that results in hospitalization should be recorded on the medical history. The hospitalization would not result in the event or condition being reported as a study-related SAE unless, in the view of the study physician, hospitalization was prolonged as a result of participation in the clinical trial or

was necessary due to a worsening of the pre-existing condition. This is because the onset of the event (the reason for the procedure) occurred before the participant was entered in the trial. Hospitalization for cosmetics, non-emergency prophylaxis, or abortion does not result in an SAE report unless, in the view of the study physician, hospitalization for these procedures was prolonged as a result of participation in the clinical trial.

8.4 Medical Emergencies

The sessions will be conducted in a private practice setting, 3.3 miles away from the East Cooper Medical Center where emergency equipment is immediately available. The study physician will be available in the case of medical emergencies and will be within three miles away from the study site during Experimental Sessions. The therapists or study physician will be available via mobile phone or pager throughout the study if any problem occurs when a PTSD+ participant or CSO participant is not at the site, and they will continue to see their outside therapist as needed throughout the study. For a recently completed Phase 2 trial, the sponsor has established contingency plans for responding to those AEs that appear most likely, based on a comprehensive review of literature described in the current IB. Similar contingency plans will be used in this protocol. The site will provide an Automated External Defibrillator (AED). The at least one therapist on each team will maintain BLS certification.

With these personnel and equipment, the therapists or study physician will be able to perform basic cardiac life support if necessary and call Emergency Medical Services (EMS) to transport the participant to the ED at the closest hospital. In the event of a medical emergency or any other medical problem, the study physician will be immediately available by phone, and based on his assessment of the situation, he will make the decision to either evaluate the participant himself at the site or have the therapists call EMS to transport the participant to the ED.

8.5 Adverse Event Collection

The study physician will be responsible for reviewing and confirming all AEs and SAEs collected during the study. The therapists will collect AEs during study/telemedicine visits after enrollment.

All SAEs will be collected for the duration of the protocol. All SAEs which occur during the course of the trial, whether considered to be associated with the study drug or not, have to be reported within 24 hours of the Clinical Investigator's awareness of their occurrence. All SAE reports should be faxed to the sponsor. A fax number will be provided to the site in separate site-specific instruction for SAE reporting. In addition to the fax, the study physician, Clinical Investigator, or designee should call the CRA during normal working hours and verbally inform the CRA of the SAE. During off business hours or if medical advice is needed immediately please call the sponsor Medical Monitor. An SAE reporting instruction with all contact numbers will be provided to the site prior to study start.

Medical Monitor:

Page 69 of 89

[name]. [name] [name] [name] [contact]

Study Monitor contact information will be provided in a separate contact list.

Adverse events that will be collected for the duration of the protocol are:

- All SAEs will be collected through participant termination
- All AEs and spontaneously reported reactions will be collected on the day of drug administration and for seven days after each Experimental Session
- Any spontaneously reported reactions that have not resolved to the PTSD+ participant's or CSO participant's Baseline level of severity after seven days will be collected on the Adverse Event Report page until resolution
- Events requiring medical attention will be collected from enrollment through the PTSD+ participant's or CSO participant's last follow-up
- Events related to planned treatments or physician visits for Baseline conditions collected in the Medical History will not be collected unless there is an exacerbation of the condition
- Any Adverse Event leading to withdrawal from the protocol will be collected throughout the study
- All AEs related to changes in psychiatric status will be collected throughout the study

A memory aid card will be provided to the participants on the last visit prior to the 3-month Follow-up to record information on medications taken to treat SAEs, AEs leading to withdrawal and psychiatric AEs during the follow-up period. The memory aid card will not be collected, but information from the card will be used to aid the participants in providing information to the Clinical Investigator. This information may be collected by phone.

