- Suicidal ideation and behavior will be assessed with the Columbia Suicide Severity Rating Scale (C-SSRS) according to the Table 3: Time and Events.
- During Experimental Sessions, Subjective Units of Distress (SUD) and vital signs including blood pressure, heart rate, and temperature will be collected.
- Serious Adverse Events (SAEs) will be collected in both groups through Study Termination. All Adverse Events (AEs) will be collected on the day of drug administration through the Primary Endpoint and will be followed to resolution.

Page 5 of 89

- Any spontaneously reported reactions will be collected from the day of the Experimental Session through seven days after both Experimental Sessions.
 Reactions that have not resolved to Baseline level of severity after seven days will be collected on the Adverse Event Report page until resolution.
- Assess General Wellbeing (clinician-rated) at all visits and phone calls for both participants.
- AEs requiring medical attention will be collected through Study Termination.
- Events related to planned treatments or physician visits for Baseline conditions collected in the Medical History will not be collected unless there is an exacerbation of the condition.
- Any AE leading to withdrawal from the protocol will be collected throughout the study.
- All AEs related to changes in psychiatric status will be collected throughout the study.
- Baseline medications and changes to psychiatric medications will be collected throughout the study.
- Changes in pre-existing chronic pain and/or tinnitus symptoms will be collected throughout the study using a Visual Analog Scale in any members of the dyad reporting these symptoms.

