Subjective Units of Distress				✓							✓								
C-SSRS	✓		✓F	✓ B, C, D	✓					✓	✓ B, C, D	✓					✓	✓	✓
SAEs, AEs of psychiatric status or withdrawal		✓	✓	✓	✓	✓	✓	✓	✓	✓	✓	✓	✓	✓	✓	✓	✓	✓	✓
AEs Requiring Medical Attention				✓	✓	✓	✓	✓	✓	✓	✓	✓	✓	✓	✓	✓	✓	✓	✓
Spontaneously Reported Reactions				✓	✓	✓	✓				✓	✓	✓	✓					
All AEs		✓	✓	✓	✓	✓	✓	✓	✓	✓	✓	✓	✓	✓	✓	✓	✓		

- A = Performed locally.
- B = At the beginning of the session.
- C = Approximately 6 hours after administration of MDMA.
- D = As needed.
- E = Approximately every 60 minutes.
- F = Given after medication washout.
- G = For 7 days after Experimental Session, contact will be made by phone or telemedicine and not both, C-SSRS D2 and D7 of calls only, General Wellbeing for all 7 days.
- H = Only in participants with pre-existing chronic pain or tinnitus.
- I = CAPS may be recorded to video.
- J = Additional time allowed if necessary for medication tapering.

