Cardiovascular effects will be assessed via blood pressure and pulse measurement. Blood pressure, body temperature, and pulse will be measured at the outset of the Experimental Session, once prior to administration of the supplemental dose, and at the end of the Experimental Session, or until it returns to near baseline levels. The timing of these measurements will be adjusted so they do not interfere with the therapeutic process. Blood pressure will be measured more frequently if there are symptoms, such as chest pain, shortness of breath or neurological symptoms or any other signs or symptoms that may be indicative of a medical complication.

A 100-millimeter visual analog scale will be used to assess changes in symptoms of preexisting tinnitus and/or chronic pain [173-175]. The Changes in Tinnitus and/or Pain visual analog scale will allow rating of symptom severity from "None" to "Worst Case Imaginable". This exploratory measure will enable quantification of subjective somatic symptoms that are known to be associated with PTSD [174, 176-178]. Presence of chronic pain is associated with PTSD, possibly as a result of psychological response to traumatic stress as reflected in brain activity, such as increased amygdalar activity in response to pain and transmitter systems involved in the stress response [174, 177, 178]. Both the PTSD+ participant and the CSO participant will be evaluated for Somatic Symptoms.

All AEs and spontaneously reported reactions will be collected, as described in Section 8.5. AEs and spontaneously reported reactions may be collected during face-to-face visits or over the telephone. Common reactions that are spontaneously reported are collected for seven days after each Experimental Session on a separate CRF page and will be categorized as mild, moderate, or severe. The researchers will ask participants about thoughts about killing or harming themselves at these visits and during the second and seventh day of telephone contact with the study therapists.

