5.2.2 Preparatory Psychotherapy Session (Visit 1 - Telemedicine Visit)

(Less than 4 weeks prior to Visit 2)

Participants who do not complete all screening activities will not be enrolled. Eligibility may be discussed by phone after screening is complete and at the time Visit 1 is scheduled but the final confirmation will occur at Visit 1. If all Inclusion Criteria and no Exclusion Criteria are met, eligibility will be confirmed with the participant.

- a. Complete a final review of Inclusion and Exclusion Criteria
- b. Assess General Wellbeing
- c. Confirm eligibility and willingness to participate in study
- d. Enroll participant and issue dyad number
- e. Ensure medical history and medication history is complete. After enrollment new events will be collected as AEs and new medications, as described in Sections 8.0 and 9.0.
- f. Discuss medication tapering, if applicable. Upon confirmation of eligibility, the PI or another designated study physician will consult the prescribing physician to initiate medication tapering for the PTSD+ participant and the CSO participant, if applicable, who must refrain from taking a psychiatric medication for the study. The prescribing physician's opinion about medication discontinuation will documented either in writing from the prescribing physician, or in writing by the study physician documenting phone contact with the prescribing physician. Tapering will follow a time course appropriate for the medication given its half-life, with the first Experimental Session scheduled to occur after complete washout. Individuals using opiates for pain management will be asked to decrease the dose or avoid taking their pain medication for 24 hours prior to Experimental Sessions if possible, as these medications may reduce the efficacy of MDMA. Participants will be permitted to take their prescribed opiate medication during this period if necessitated by pain flare-ups.

This first Preparatory Session will last 90 minutes and take place at Visit 1. During the Preparatory Sessions:

- a. This visit may be conducted by telemedicine or phone.
- b. Therapists may record all sessions to audio and video. The PTSD+ participant and the CSO participant will be given access to review audio or video recordings from the sessions upon request.

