8.2 Spontaneously Reported Reactions

Commonly expected spontaneously reported reactions are collected on a separate CRF page and will be categorized as mild, moderate, or severe. Common, expected reactions are defined as those most frequently reported in the literature and include: Anxiety, Diarrhea, Difficulty Concentrating, Dizziness, Drowsiness, Dry Mouth, Fatigue, Headache, Heavy Legs, Impaired Gait/Balance, Impaired Judgment, Increased Irritability, Insomnia, Jaw Clenching or Tight Jaw, Lack of Appetite, Low Mood, Muscle Tension, Nausea, Need More Sleep, Nystagmus, Parasthesias, Perspiration, Restlessness, Rumination (increased private worries), Sensitivity to Cold, Thirst, and Weakness. Spontaneously reported reactions will be collected during the Experimental Session and the seven days of telephone contact following the Integrative Session that occurs on the day after each Experimental Session. Each reported reaction will be actively followed during follow-up phone calls or visits until resolution. Any reported event that is not listed as a Spontaneously Reported Reaction will be collected as an Adverse Event following the plan in Section 8.5 Adverse Event Collection. Any common reaction lasting longer than seven days will be tracked as an adverse event in order to obtain a resolution date.

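### Protocol 8.5 limits collection of all adverse events to the drug day plus seven days per session, while the synopsis, Protocol 3.4, SAP 3.4 and Table 3 run to the Primary Endpoint

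*Protocol*

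**What the plan says.** **The short window.** One bullet in Protocol 8.5 reads: "All AEs and spontaneously reported reactions will be collected on the day of drug administration and for seven days after each Experimental Session". All AEs and reactions are the joint subject of that sentence, so the time limit applies to both.

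**The long window.** The Protocol synopsis (Safety), Protocol 3.4 and SAP 3.4 carry the same sentence: "All Adverse Events (AEs) will be collected on the day of drug administration through the Primary Endpoint and will be followed to resolution". In Table 3 of both documents the row for all AEs is ticked at every visit from V1 to V16 and is blank at V17 and V18.

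**Statements with no stop at V16.** The opening of 8.5 says: "The therapists will collect AEs during study/telemedicine visits after enrollment". Section 5.2.2 (Visit 1) says: "After enrollment new events will be collected as AEs and new medications, as described in Sections 8.0 and 9.0". Section 5.2.9 orders AE collection at V17 and V18, again by reference to Sections 8.0 and 9.0.

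**What 8.5 keeps beyond the seven days.** It keeps SAEs, AEs leading to withdrawal, AEs related to psychiatric status, and reactions still unresolved after seven days. It also keeps events needing medical care: "Events requiring medical attention will be collected from enrollment through the PTSD+ participant's or CSO participant's last follow-up".

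**Pointers.** Section 5.1.2 says: "All AEs and spontaneously reported reactions will be collected, as described in Section 8.5". Section 8.2 says that an event not on the reaction list "will be collected as an Adverse Event following the plan in Section 8.5 Adverse Event Collection".

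**The concern.** A site that looks up the AE rule is sent to Section 8.5 and finds a window that closes seven days after each session. A site that works from Table 3 or Section 3.4 records every AE to V16. Both would be following the protocol, yet they would produce different AE data.

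Take a new, mild headache 12 days after V3 that needs no care. Headache is a listed reaction, but the reaction window has closed and this is not an unresolved one. Under the literal 8.5 bullet it is not recorded. Under 3.4 and Table 3 it is an AE.

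The stake is the safety tables. SAP section 6 makes AE reports the primary measure of safety and defines the analysed AEs as those occurring after dosing, plus worsened medical history, without an end date. The content of the incidence tables therefore depends on which collection rule the site used. With 10 participants per role, one participant whose only event under a preferred term goes unrecorded moves that term's incidence by 1/10, or 10 percentage points, in that role group (1/20, or 5 points, in the total sample).

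**Working it through.** **Step 1. The rules side by side**

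| Source | Start for all AEs | End for all AEs |
|---|---|---|
| Protocol 8.5, bullet | Drug day | Seven days after each session |
| Synopsis, Protocol 3.4, SAP 3.4 | Drug day | Primary Endpoint |
| Table 3, both documents | V1 | V16 |
| Protocol 8.5, lead sentence | After enrollment | None stated |
| Protocol 5.2.2 | After enrollment | None stated |
| Protocol 5.2.9 | (ordered at V17, V18) | None stated at V16 |

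The bullet is the only rule that closes between the drug day and V16. The other sources also disagree among themselves, on the start (drug day or enrollment) and on the end (V16 or no stated stop).

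**Step 2. Does another passage settle it?** Sections 5.1.2 and 8.2 point to 8.5. The instructions for V2, V5 to V8, V9, V12 to V15, V16 and V17 to V18 all order AE collection, but by reference to Sections 8.0 and 9.0, and so back to the section with the conflict. SAP 4.0 makes the protocol the definitive reference, which cannot resolve a conflict inside the protocol.

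**Step 3. Days in dispute.** The documents give no figure to reproduce. Inputs:
- V3 is day 1 (Table 3).
- V10 is 3 weeks later (Protocol 4.0): 1 + 21 = day 22.
- V15 closes the 4 weeks after V10 (section on Integrative Sessions Between Experimental Sessions): 22 + 28 = day 50.
- V16 is 30 days after V15, window -2/+7 (5.2.8): 50 + 30 = day 80, range 78 to 87.

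*Count A: drug day plus seven days, as 8.5 is worded.* The section on daily telephone contact starts the contacts on the day after the session, which gives the same eight days.
- Covered: days 1–8 and 22–29, 8 + 8 = 16 days.
- Outside: days 9–21 (13) plus days 30–80 (51) = 64 of 80 days, or 80%.

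*Count B: seven days counted after the next-day Integrative Session, as 8.2 can be read for reactions.*
- Covered: days 1–9 and 22–30, 9 + 9 = 18 days.
- Outside: 80 − 18 = 62 of 80 days, or 77.5%.

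*With the V16 window:*

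| V16 on day | Count A | Count B |
|---|---|---|
| 78 | 78 − 16 = 62 | 78 − 18 = 60 |
| 80 | 80 − 16 = 64 | 80 − 18 = 62 |
| 87 | 87 − 16 = 71 | 87 − 18 = 69 |

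The range is 60 to 71 days.

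**Step 4. Which events are exposed on those days?** Remove from all AEs the categories that 8.5 keeps open. What remains is AEs that are non-serious, not psychiatric, need no medical attention, do not lead to withdrawal and are not unresolved reactions.

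**Step 5. Medication records.** From seven days after the last session to Study Termination, Section 9.0 records medications, including over-the-counter products, only where they treat AEs, and it cites 8.5. Under the literal bullet, a minor AE self-treated in that period could leave a medication entry with no matching AE. This is partial support only. Section 9.0 runs past V16, so the same mismatch can arise after V16 under any rule that ends at the Primary Endpoint.

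**The case against.** The best defence is that no careful site would stop at day seven. The bullet does not say that AEs are collected only then, whereas Section 9.0 does use a restricting word when it narrows medication recording. The pointers cite Section 8.0 or 8.5 as a whole, including the lead sentence, and not this one bullet. Recording AEs at every visit to V16 breaches no sentence in the protocol, and the visit instructions order AE collection at each of those visits. The exposed class is minor by definition, in an open-label pilot of 10 dyads that is not intended to lead to registration.

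Much of this stands. It is likely that AEs would be asked about, and the restriction is an inference from how the list is built: a short window for all AEs next to study-long windows for selected categories. But if all AEs were to be collected to V16 anyway, the bullet's time limit on them would do no work. The text supports two readings, and nothing else in either document chooses between them.

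Three stronger readings do not hold.
- A reader might infer that about 80% of AE follow-up is lost. The day count only shows where the rules differ. Most clinically important categories are collected throughout, and the documents give no rate for the remaining class.
- A reader might infer that the bullet is the only departure and that every other source agrees after dosing. The 8.5 lead sentence, 5.2.2 and 5.2.9 state no stop at V16.
- A reader might infer from Section 9.0 that correcting the bullet would tie every recorded medication to an AE. After V16 it would not.

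**Conclusion.** The contradiction is real and should be corrected. It leaves unclear whether a narrow class of minor post-dose AEs is recorded on 62 to 64 of the nominal 80 days from first dose to the Primary Endpoint, or on 60 to 71 days with the V16 window and either way of counting the seven days. The number of events affected cannot be estimated from the documents.

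The day count assumes nominal visit spacing. Section 4.1 lets delays between visits extend the study, which would lengthen the disputed period. The incidence arithmetic assumes 10 treated participants per role.

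The effect is confined to the completeness of the AE tables. Collection of SAEs and psychiatric AEs is not in doubt, and the primary CAPS-5 analysis is untouched.

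**What to change.** 1. Split the 8.5 bullet. Keep the drug-day-plus-seven-days limit for spontaneously reported reactions only, and add a separate bullet that all AEs are collected through the Primary Endpoint (V16). This follows Protocol 3.4, which already gives AEs and reactions separate windows.
2. Choose one start point for all AEs and use it in 8.5, the synopsis, Protocol 3.4, SAP 3.4 and Table 3. Enrollment would match Table 3 and 5.2.2. Pre-dose events could then be listed separately, because the SAP analyses AEs after dosing and worsened medical history.
3. State in 5.2.9 that AE collection at V17 and V18 covers only the categories that 8.5 and Table 3 continue after V16: SAEs, events requiring medical attention, AEs leading to withdrawal, psychiatric AEs and unresolved reactions.
4. Optional tidy-up: the Table 3 row "AEs Requiring Medical Attention" starts at V3, while 8.5 and the SAP start at enrollment. No data are lost under Table 3 as it stands, because its row for all AEs covers V1 and V2.

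The cost is a few wording edits in the two documents and slightly more AE recording at visits already scheduled. No visits or assessments are added.
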